5.1 Inclusion criteria

Patients eligible for inclusion in this study must fulfill all of the following criteria:

1. Patient must be able to understand and communicate with the investigator and comply with the requirements of the study and must provide written, signed and dated informed consent before any study assessment is performed.
2. Male or non-pregnant, non-lactating female patients at least 18 years of age.
3. Diagnosis of axSpA (either r-axSpA (AS) or nr-axSpA) fulfilling the ASAS classification criteria for axSpA ([Appendix 2](#)).
4. Active disease as defined by having an ASDAS ≥ 2.1 at Screening and Baseline despite concurrent NSAID therapy, or intolerance/contraindication to NSAIDs.
5. Objective signs of inflammation at Screening as defined by:
MRI of sacroiliac joints performed up to 3 months prior to screening showing acute inflammatory lesion(s),
OR
elevated quick CRP (> 5 mg/L),
OR
MRI showing acute inflammatory lesion(s) in the sacroiliac joints performed during screening period.
6. Patients should have been on at least 2 different NSAIDs at the highest recommended dose for at least 4 weeks (in total) in the past, with an inadequate response or failure to respond, or less if therapy had to be reduced due to intolerance, toxicity or contraindications.
7. Patients who are regularly taking NSAIDs (including cyclooxygenase-1 [COX-1] or cyclooxygenase-2 [COX-2] inhibitors) as part of their axSpA therapy are required to be on a stable dose for at least 1 week before randomization.
8. Patients taking MTX (7.5 mg/week to 25 mg/week) or sulfasalazine (≤ 3 g/day) are allowed to continue their medication but are required to be on a stable dose for at least 4 weeks before randomization.
9. Patients who are on a DMARD other than methotrexate (MTX) or sulfasalazine must discontinue the DMARD 4 weeks prior to randomization.
10. Patients taking corticosteroids must be on a stable dose of ≤ 10 mg/day prednisone or equivalent for at least 2 weeks before randomization and should remain on a stable dose up to Week 24.

5.2 Exclusion criteria

Patients fulfilling **any** of the following criteria are not eligible for inclusion in this study. No additional exclusions may be applied by the investigator, in order to ensure that the study population will be representative of all eligible patients.

1. Chest X-ray or chest MRI with evidence of ongoing infectious or malignant process obtained within 3 months prior to Screening and evaluated by a qualified physician.
2. Previous exposure to secukinumab or other biologic drug directly targeting IL-17 or IL-17 receptor.
3. Patients who have previously been treated with TNF α inhibitors (investigational or approved).
4. Patients taking high potency opioid analgesics (e.g. methadone, hydromorphone, morphine).
5. Previous treatment with any cell-depleting therapies including but not limited to anti-CD20 or investigational agents (e.g. CAMPATH, anti-CD3, anti-CD4, anti-CD5, anti-CD19).
6. History of hypersensitivity to secukinumab or adalimumab or their excipients or to drugs of similar chemical classes.
7. Contraindications for secukinumab or adalimumab.
8. Inability or unwillingness to undergo MRI (e.g. patients with pacemakers, aneurysm clips or metal fragments / foreign objects in the eyes, skin or body that are not MRI compatible) in case MRI is not already available (maximum 3 months old).
9. Use of any investigational agents within 4 weeks or within 5 half-lives of the drug (whichever is longer) prior to the Baseline Visit.
10. Pregnant or nursing (lactating) women, where pregnancy is defined as the state of a female after conception and until the termination of gestation, confirmed by a positive human chorionic gonadotropin (hCG) laboratory test.
11. Women of child-bearing potential, defined as all women physiologically capable of becoming pregnant, unless they are using effective methods of contraception during dosing of study treatment and minimum 16 weeks or longer if local label requires it after the last dose (e.g. 20 weeks for secukinumab, 5 months for adalimumab in the European Union). Effective contraception methods include:
 - Total abstinence* (when this is in line with the preferred and usual lifestyle of the patient. Female sterilization (have had surgical bilateral oophorectomy with or without hysterectomy), total hysterectomy or tubal ligation at least 6 weeks before taking investigational drug. In case of oophorectomy alone, only when the reproductive status of the woman has been confirmed by follow-up hormone level assessment).
 - Male sterilization (at least 6 months prior to Screening). For female patients on the study, the vasectomized male partner should be the sole partner for that patient.
 - Barrier methods of contraception: condom or occlusive cap (diaphragm or cervical/vault caps).
 - Use of oral (estrogen and progesterone), injected, or implanted hormonal methods of contraception or other forms of hormonal contraception that have comparable efficacy

(failure rate < 1%), for example hormone vaginal ring or transdermal hormone contraception or placement of an intrauterine device or intrauterine system.

* Periodic abstinence (e.g. calendar, ovulation, symptothermal, post-ovulation methods) and withdrawal are not acceptable methods of contraception.

In case of use of oral contraception women should have been stable on the same pill for a minimum of 3 months before taking investigational drug.

In case local regulations deviate from the contraception methods listed above, local regulations apply and will be described in the informed consent form (ICF).

Women are considered post-menopausal and not of child bearing potential if they have had 12 months of natural (spontaneous) amenorrhea with an appropriate clinical profile (e.g. age appropriate, history of vasomotor symptoms) or have had surgical bilateral oophorectomy (with or without hysterectomy), total hysterectomy or tubal ligation at least 6 weeks ago. In the case of oophorectomy alone, only when the reproductive status of the woman has been confirmed by follow up hormone level assessment is she considered not of child-bearing potential.

12. Active ongoing inflammatory diseases other than axSpA that might confound the evaluation of the benefit of secukinumab therapy, including inflammatory bowel disease or uveitis.
13. Underlying metabolic, hematologic, renal, hepatic, pulmonary, neurologic, endocrine, cardiac, infectious or gastrointestinal conditions, which in the opinion of the investigator immunocompromises the patient and/or places the patient at unacceptable risk for participation in an immunomodulatory therapy.
14. Significant medical problems or diseases, including but not limited to the following: uncontrolled hypertension ($\geq 160/95$ mmHg), congestive heart failure (New York Heart Association status of class III or IV) and uncontrolled diabetes.
15. History of clinically significant liver disease or liver injury as indicated by abnormal liver function tests such as aspartate aminotransferase (AST), alanine aminotransferase (ALT), alkaline phosphatase or serum bilirubin. The investigator should be guided by the following criteria:
 - a. Any single parameter may not exceed 2 x upper limit of normal (ULN). A single parameter elevated up to and including 2 x ULN should be re-checked once more as soon as possible and in all cases, at least prior to enrollment/randomization, to rule out any possible laboratory error.
 - b. If the total bilirubin concentration is increased above 2 x ULN, total bilirubin should be differentiated into the direct and indirect reacting bilirubin.
16. History of renal trauma, glomerulonephritis, or patients with one kidney only, or a serum creatinine level exceeding 1.8 mg/dL (159.12 μ mol/L).
17. Laboratory results at screening visit: total white blood cell (WBC) count $< 3000/\mu\text{L}$, or platelets $< 100\,000/\mu\text{L}$ or neutrophils $< 1500/\mu\text{L}$ or hemoglobin $< 8.3\text{ g/dL}$ (83 g/L).
18. Active systemic infections during the last 2 weeks (exception: common cold) prior to randomization.
19. History of ongoing, chronic or recurrent infectious disease or evidence of TB infection as defined by a positive result is defined as an induration of ≥ 5 mm or according to local

practice/guidelines) or a positive QuantiFERON TB-Gold test. Patients with a positive test may participate in the study if further work up (according to local practice/guidelines) establishes conclusively that the patient has no evidence of active TB. If presence of latent TB is established, then treatment according to local country guidelines must have been initiated prior to randomization.

20. Patients positive for human immunodeficiency virus, hepatitis B or hepatitis C at randomization.
21. History of lymphoproliferative disease or any known malignancy or history of malignancy of any organ system within the past 5 years (except for basal cell carcinoma or actinic keratoses that have been treated with no evidence of recurrence in the past 3 months, carcinoma *in situ* of the cervix or non-invasive malignant colon polyps that have been removed).
22. Live vaccinations within 6 weeks prior to Baseline or planned vaccination during study participation until 12 weeks after last study treatment administration.
23. Current severe progressive or uncontrolled disease which in the judgment of the clinical investigator renders the patient unsuitable for the trial.
24. Inability or unwillingness to undergo repeated venipuncture (e.g. because of poor tolerability or lack of access to veins).
25. Any medical or psychiatric condition which, in the investigator's opinion, would preclude the participant from adhering to the protocol or completing the study per protocol.
26. Donation or loss of 400 mL or more of blood within 8 weeks before randomization.
27. History or evidence of ongoing alcohol or drug abuse, within the last 6 months before randomization.

6 Treatment

6.1 Study treatment

Investigational treatment – treat-to-target regimen

[figure not shown]
- **Secukinumab 150 mg**, liquid formulation in 1 mL prefilled syringe (PFS) for s.c. injection – all patients will receive 150 mg dose at Baseline, Week 1, 2, 3, 4 and 8. From Week 12, only responders (i.e. patients with ASDAS clinically important improvement, defined as change from Baseline ≥ 1.1) will continue to receive 4-weekly doses until Week 32 if they maintain the response.
- **Secukinumab 300 mg**, liquid formulation in 2 \times 1 mL PFS for s.c. injection – patients who are non-responders at Week 12 will receive 4-weekly doses until Week 20. From Week 24, only responders will continue to receive 4-weekly doses until Week 32.
- **Secukinumab 300 mg as escape treatment**, liquid formulation in 2 \times 1 mL PFS for s.c. injection - patients who were responders at Week 12, but experienced a loss of response (defined as ASDAS change from Baseline < 1.1) at Week 24 will receive 4-weekly 300 mg doses until Week 32.
- **Adalimumab biosimilar (Hyrimoz®) 40 mg**, liquid formulation in 0.8 mL PFS for s.c. injection – patients who are **non-responders to secukinumab 300 mg** at Week 24 will

receive from this time point biweekly doses of adalimumab biosimilar (Hyrimoz®) until Week 34.

Reference treatment – standard-of-care regimen

- Patients will receive treatment according to local practice standards by their treating physician following the current treatment recommendations. Current guideline recommends to start a biological disease modifying anti-rheumatic drug (bDMARD) after the failure of the NSAIDs therapy. According to the 2016 updated Ankylosing SpondyloArthritis International Society (ASAS)/European League Against Rheumatism recommendations, current practice is to start biological therapy with a TNF α blocker. After the failure of the first biologic therapy and in case of positive opinion of the rheumatologist, a switch to another TNF α -inhibitor or to IL-17-inhibitor should be considered ([van der Heijde et al 2017](#)). In accordance with these recommendation the treatment initiation, adjustment and switch will be conducted based on the disease activity and the positive opinion of the investigator. These therapy re-arrangement can be decided and performed at the time of regular study visit (e.g. Visit week 12 or Visit Week 24) or during unscheduled visits as per clinical routine of the investigator.

Figure 6-2 The 2016 updated Ankylosing SpondyloArthritis International Society (ASAS)/European League Against Rheumatism (van der Heijde et al 2017)

ASDAS, Ankylosing Spondylitis Disease Activity Score; BASDAI, Bath Ankylosing Spondylitis Disease Activity Index; bDMARD, biological disease-modifying antirheumatic drug; TNFi, tumor necrosis factor inhibitor; IL17-inhibitor, interleukin-17 inhibitor. *Either BASDAI or ASDAS, but the same outcome per patient.

Novartis will supply the investigational treatment in an open-label manner. Patients or caregivers will be instructed by site staff on how to self-administer the s.c. injection using the PFS containing the liquid formulation of secukinumab and/or adalimumab biosimilar (Hyrimoz®). Study treatment administrations at mandatory site visits (i.e. at Baseline, Week 12 and Week 24) will be performed by the patient under the supervision of site staff. Study treatment administrations outside of these site visits can either be performed at the patient's home or at optional study visits under the supervision of site staff as described in [Section 6.7.2](#). Patients receiving secukinumab will follow the secukinumab Instructions for Use (IFU) document, and patients receiving adalimumab biosimilar (Hyrimoz®) will follow the adalimumab biosimilar (Hyrimoz®) IFU document. The IFUs for the medication in the SOC arm will be provided by the investigator in accordance with her/his clinical routine. Site staff will administer the injection to patients who are not able or feel insecure to self-administer the PFS injection.

6.1.1 Additional study treatments

No additional treatment beyond investigational and reference treatment are included in this trial.

6.1.2 Treatment arms/group

Patients will be randomly assigned at the Baseline Visit to either the T2T group or the SOC group.

T2T group (n = 150)

Starting from the Baseline Visit, patients will be treated with secukinumab 150 mg s.c. weekly until Week 4 and then at Week 8.

At Week 12:

- If ASDAS clinically important improvement is achieved and maintained, patients will continue the treatment up to Week 32 if they maintain the response.
- If ASDAS clinically important improvement is not achieved, patients will receive escalated dose of secukinumab 300 mg s.c. every 4 weeks until Week 20.

At Week 24:

Patients who are receiving secukinumab 300 mg, and

- Achieved ASDAS clinically important improvement, will continue the treatment up to Week 32.
- Did not achieve ASDAS clinically important improvement, will be switched to adalimumab biosimilar (Hyrimoz®) 40 mg s.c. every 2 weeks until Week 34.

Escape arm

- Patients who are receiving 150 mg secukinumab (i.e. were responders at Week 12) can be escalated at Week 24 to 300 mg secukinumab every 4 weeks until Week 32, if they experienced a loss of response, where loss of response is defined as ASDAS change from Baseline < 1.1.

SOC group (n = 150)

Patients will receive treatment according to local practice standards by their treating rheumatologist following the current treatment recommendations with NSAIDs as the first-choice drug treatment and DMARDs for patients with active disease despite the use (or intolerance/contraindication) of NSAIDs.

6.1.3 Treatment duration

Each patient will be treated for a maximum of 36 weeks (last dose of secukinumab at Week 32, last dose of adalimumab biosimilar (Hyrimoz®) at Week 34).

6.2 Other treatment

6.2.1 Concomitant therapy

The investigator must instruct the patient to notify the study site about any new medications he/she takes after the patient is enrolled into the study. All medications, procedures, and significant non-drug therapies (including physical therapy and blood transfusions) administered after the patient was enrolled into the study must be recorded on the appropriate case report form (CRF).

Each concomitant drug must be individually assessed against all exclusion criteria/prohibited medication. If in doubt, the investigator should contact the Novartis medical monitor before randomizing a patient or allowing a new medication to be started. If the patient is already enrolled, contact Novartis to determine if the patient should continue participation in the study.

6.2.1.1 Permitted concomitant therapy requiring caution and/or action

Methotrexate

Patients taking MTX (up to 25 mg/week) must be on a stable dose for at least 4 weeks before randomization.

Sulfasalazine

Patients taking sulfasalazine (\leq 3 g/day) must be on a stable dose for at least 4 weeks before randomization.

Systemic corticosteroids

Treatment with systemic corticosteroids is permitted if the dose was stable within the 2 weeks preceding randomization, up to a maximum daily dosage of 10 mg prednisone equivalent. Higher-dose, time-limited corticosteroid courses (bursts) may be permitted for exacerbations of medical conditions unrelated to axSpA (e.g. asthma, chronic obstructive pulmonary disease, contact dermatitis) after randomization.

Nonsteroidal anti-inflammatory drugs (including COX-1 or COX-2 inhibitors) and acetaminophen/paracetamol

Patients should have been on at least 2 different NSAIDs at the highest recommended dose for at least 4 weeks (in total) prior to randomization with an inadequate response or failure to respond, or less if therapy had to be withdrawn due to intolerance, toxicity or contraindications.

Patients regularly using NSAIDs, low strength opioids, or paracetamol/acetaminophen should be on a stable dose for at least 1 week before randomization to allow inclusion in the study.

6.2.2 Prohibited medication

6.2.2.1 Prohibited prior medication (washout periods)

Previous use of medication listed in [Table 6-1](#) is either not allowed at all or the given medication must be washed out as indicated. [Table 6-1](#) refers to both treatment arms.

Table 6-1 Prohibited prior treatments (both arms)

Prohibited prior treatments	Washout period before randomization
Biologic drugs directly targeting IL-17 or IL-17 receptor	Previous exposure at any time: exclusion criterion
TNF α inhibitors (e.g. adalimumab, infliximab, certolizumab, golimumab).	Previous exposure at any time: exclusion criterion
Any cell-depleting therapies including but not limited to anti-CD20 or investigational agents [e.g. alemtuzumab (Campath), anti-CD4, anti-CD]	Previous exposure at any time: exclusion criterion
Unstable dose of MTX or sulfasalazine	4 weeks
Other DMARD (incl. apremilast, except MTX and – in case of axSpA – sulfasalazine)	4 weeks
Leflunomide with cholestyramine washout	4 weeks
Unstable doses of NSAIDs (COX1 or COX2 inhibitors), low strength opioids, paracetamol/acetaminophen.	2 weeks
Analgesics, other than NSAIDs or paracetamol/acetaminophen or low strength opioids as described above	2 weeks
Systemic corticosteroids > 10 mg prednisone per day equivalent	2 weeks
Unstable dose of systemic corticosteroids \leq 10 mg prednisone equivalent per day	2 weeks
Any investigational treatment other than study medication or participation in any interventional trial	4 weeks or 5 half-lives (whichever is longer)
Live vaccinations	6 weeks
Medical cannabis	2 weeks

axSpA=ankylosing spondyloarthritis, COX-1=cyclooxygenase 1, COX-2=cyclooxygenase 2, DMARD=disease modifying anti-rheumatic drug, IL-17=interleukin-17, MTX=methotrexate, NSAIDs=non-steroidal anti-inflammatory drugs

6.2.2.2 Prohibited concomitant medication (T2T arm only)

Use of the treatments displayed in [Table 6-2](#) is NOT allowed after the start of the washout period (see [Table 6-1](#)) and refers to T2T arm only.

There is no prohibited concomitant treatment in SOC arm, all SOC patients should be treated at the discretion of the investigator and in accordance with current therapy recommendation.

Live vaccines should not be given until 12 weeks after the last study drug administration.

Table 6-2 Concomitant treatment in T2T arm

Prohibited treatments	Action to be taken
Biologic drugs directly targeting IL-17 or IL-17 receptor other than investigational drug	Discontinue study treatment
TNF α inhibitors (e.g. adalimumab, infliximab, certolizumab, golimumab) other than investigational drug	Discontinue study treatment
Any cell-depleting therapies including but not limited to anti-CD20 or investigational agents [e.g. alemtuzumab (Campath), anti-CD4, anti-CD	Discontinue study treatment
csDMARDs other than MTX or sulfasalazine	Protocol deviation
Leflunomide	Protocol deviation
High potency opioid analgesics (e.g. methadone, hydromorphone, morphine)	Protocol deviation
Analgesics (other than NSAIDs, paracetamol/acetaminophen or low strength opioids)	Protocol deviation
Any investigational treatment other than study medication or participation in any interventional trial	Discontinue study treatment
Systemic corticosteroids \geq 10 mg prednisone equivalent per day Local (injectable) steroids: > 2 injections or >80 mg triamcinolone equivalent in total.	Dose increase should be avoided; dose reduction at the investigator's discretion
NSAIDs (including COX-1 and COX-2 inhibitors)	Dose increase should be avoided; dose reduction at the investigator's discretion
MTX or sulfasalazine	Dose increase should be avoided; dose reduction at the investigator's discretion
Live vaccinations	Discontinue study treatment
Medical cannabis	Protocol deviation

COX-1=cyclooxygenase 1, COX-2=cyclooxygenase 2, DMARD=disease modifying anti-rheumatic drug, IL-17=interleukin-17, MTX=methotrexate, NSAIDs=non-steroidal anti-inflammatory drugs, TNF α =tumor necrosis factor alpha

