Neutropenia was more frequently observed with secukinumab than with placebo, but most cases were mild, transient, and spontaneously reversible.

The incidence of hypersensitivity AEs was slightly higher with secukinumab compared with placebo, with the difference mostly due to mild to moderate urticaria and eczema not associated with systemic symptoms.

The incidence of selected rare events of interest (major adverse cardiovascular events and malignancies) adjusted for exposure over 52 weeks was comparable to placebo in clinical trials across multiple indications.

There was no clear association between treatment with secukinumab and new onset of inflammatory bowel disease but due to the potential involvement of the interleukin-17 (IL-17) pathway in the pathogenesis of the disease, it is not possible to rule out a potential increased risk of exacerbation.

Secukinumab 300 mg was comparable to 150 mg and both doses showed comparable safety to placebo and etanercept over 52 weeks of treatment.

Infections, neutropenia, and hypersensitivity are important identified risks, while malignancies, major adverse cardiovascular events, immunogenicity, Crohn's disease, and hepatitis B reactivation are important potential risks. Interaction with live vaccines is an important potential interaction (and also included as an important potential risk).

No new identified risks were reported. During the reporting interval, a Risk Management Plan (RMP) update was triggered upon request from Pharmacovigilance Risk Assessment Committee, to include suicidal ideation and behavior (SIB) as an important potential risk in the RMP on the basis that "although causality has not been established, SIB meets the criteria as important potential risk because a potential biological mechanism cannot be completely ruled out since the biological role of IL-17 receptor ligands is still largely unknown, and consideration of the potential public health impact". The RMP is currently being updated for this change. At its completion SIB will be listed as an important potential risk in the RMP.

No new safety signal was identified and no actions were taken for safety reasons during the reporting period of the latest drug safety update report.

The risk to patients in this trial will be minimized by compliance with the eligibility criteria, close clinical monitoring, and extensive guidance to the investigators, provided in the current version of the Investigator's Brochure (IB).

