6.5 Permitted dose adjustments and interruptions of study treatment

In the T2T arm study treatment dose adjustments are not permitted. Study treatment interruption is also not permitted with the following exception:

- Study treatment interruption is only permitted if, in the opinion of the investigator, a patient is deemed to be at a significant safety risk unless administration of investigational treatment is temporarily interrupted. In such cases study treatment should be interrupted

only during the time that this risk is present and ongoing. Study treatment can be restarted at the next scheduled visit after resolution of the safety risk.

The effect of secukinumab or adalimumab biosimilar (Hyrimoz®) on live vaccines is unknown; therefore live vaccines should not be administered during participation in the study. The elimination of adalimumab may take up to 4 months ([Humira® SmPC](#)); in case a live vaccine has been administered due to a medical urgency, study treatment should be discontinued

Treatment and thus any dose adjustments and/or treatment interruption and/or permanent discontinuations in the SOC arm are at the discretion of the investigator.

Study treatment/reference treatment interruption or permanent discontinuation of study treatment/reference treatment will not affect the ability of the patient to remain in the study.

Any study treatment interruption must be recorded on the corresponding CRF.

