9.2 Study completion and post-study treatment

A patient will be considered to have completed the study when the patient has completed the last visit planned in the protocol i.e. Follow-up Visit /Week 56 (see [Table 8-1](#)). Information on the patient's completion or discontinuation from the study and the reason for discontinuation from the study will be recorded on the appropriate Study Phase Completion page in the eCRF.

The investigator must provide follow-up medical care for all patients who are prematurely withdrawn from the study or must refer them for appropriate ongoing care. This care may include initiating another treatment outside of the study as deemed appropriate by the investigator. Based on the individual risk/benefit profile of a patient, treatment options may include DMARDs.

In case of follow-up medical care with a biologic treatment the waiting period before initiating treatment will be at the discretion of the investigator or a minimum of 5-half-lives of the selected biologic treatment, whichever is longer.

10 Safety monitoring and reporting

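### The protocol gives two end points for the live-vaccine restriction in the T2T arm, 10 to 12 weeks apart for patients dosed on schedule, and does not say which governs

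*Protocol*

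**What the plan says.** Four parts of the protocol bear on how long live vaccines are to be avoided.

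- **Section 6.2.2.2** (prohibited concomitant medication, T2T arm only): "Live vaccines should not be given until 12 weeks after the last study drug administration". Table 6-2 in the same section lists live vaccinations and gives one action, stopping study treatment.
- **Section 5.2, exclusion criterion 22**, repeated in the protocol summary, excludes patients with "planned vaccination during study participation until 12 weeks after last study treatment administration".
- **Section 6.5** (dose adjustments and interruptions) says that the effect of either T2T drug on live vaccines is unknown, "therefore live vaccines should not be administered during participation in the study". It gives no 12-week limit. It adds: "The elimination of adalimumab may take up to 4 months".
- **Section 4.4** explains why the restriction exists: "Interaction with live vaccines is an important potential interaction". It is also listed there as a potential risk.

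The timing comes from two further sections. Section 6.1.3 gives the "last dose of secukinumab at Week 32, last dose of adalimumab biosimilar (Hyrimoz®) at Week 34". Section 9.2 counts a patient as having completed the study only after "the last visit planned in the protocol i.e. Follow-up Visit /Week 56".

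**The concern.** Sections 6.2.2.2 and 6.5 address the same act in the same patients and stop at different times. The first counts from the last dose. The second runs with study membership, which continues through a 20-week safety follow-up period. For a T2T patient in that period, a site working from the concomitant-medication section would take the restriction as over at a date when section 6.5 still applies it. The protocol names live-vaccine interaction as a safety matter, so the advice given to patients and the judgement of whether the protocol was followed should not turn on which section a site consulted.

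There is a second mismatch. The 12-week end point is shorter than the adalimumab elimination time that the protocol itself gives in 6.5, and no section explains how the two fit together.

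**Working it through.** No sample size, power or error rate is involved. The check is calendar arithmetic.

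**Inputs**
- Last dose: Week 32 for secukinumab, Week 34 for adalimumab biosimilar (6.1.3).
- Time-since-dose rule: 12 weeks (6.2.2.2; exclusion 22 for planned vaccination).
- Participation rule: to the end of participation (6.5).
- End of participation: follow-up visit 20 weeks after Week 36 (section 3; 9.2).
- Adalimumab elimination: up to 4 months (6.5).

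**The plan's own figure.** 36 + 20 = Week 56, as stated.

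**Patients dosed on schedule.** Difference = 56 − (week of last dose + 12).

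| Last T2T drug | Last dose | 12-week rule ends | Participation rule ends | Difference |
|---|---|---|---|---|
| Secukinumab | Week 32 | 32 + 12 = Week 44 | Week 56 | 12 weeks |
| Adalimumab biosimilar | Week 34 | 34 + 12 = Week 46 | Week 56 | 10 weeks |

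**Treatment stopped early, patient stays in the study.** Section 6.5 allows this. The same formula gives 56 − (L + 12) = 44 − L weeks for a last dose at Week L. A last dose at Week 8 gives 36 weeks, and a last dose at Week 20 gives 24 weeks.

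**Patient leaves the study early and attends both closing visits.** Section 3 places these 4 weeks after the last dose and a further 20 weeks later. The difference is 4 + 20 − 12 = 12 weeks.

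**Against the elimination statement.** Four months is 4 × 365.25 / 12 / 7 = 17.4 weeks. Counted from a Week 34 dose, it ends at 34 + 17.4 = Week 51.4. The 12-week rule ends at Week 46, which is 51.4 − 46 = 5.4 weeks sooner. The participation rule ends 56 − 34 = 22 weeks after that dose, which is later than 17.4 weeks.

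**Precedence.** None of the sections cited says whether 6.2.2.2 or 6.5 governs, or that the later date applies.

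**The case against.** The strongest reply is that the two rules can both be obeyed. Section 6.2.2.2 sets a minimum wait, and nothing in it expressly permits a vaccine once 12 weeks have passed. Section 6.5 adds a restriction tied to participation. A site that waits for the later date satisfies both. This stands, so a reader who infers that a vaccine is at once allowed and forbidden in the interval goes further than the text: permission after 12 weeks is an inference from silence. It does not remove the problem, because no section tells a site to apply the later date. On that reading the 12-week sentence would also do nothing for any patient followed to the planned final visit.

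Other parts of the reply also stand.

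- Exclusion 22 is an eligibility rule about vaccination planned at entry, and its wording mentions participation as well as the 12 weeks. The operational mismatch is between 6.2.2.2 and 6.5.
- Section 6.2.1 sends doubtful concomitant treatments to the sponsor's medical monitor. This helps a site that notices the discrepancy, but not one that has read only 6.2.2.2 and has no doubt.
- New medications are recorded (6.2.1), and adverse events are followed for at least 20 weeks after the last dose (10.1.1). A reader might infer that a vaccine given in follow-up would go unseen, and these sections do not support that. Table 6-2's action has no effect after the last dose, but that is missing detail, not a contradiction.
- The elimination mismatch arises only if the 12-week rule is read alone. It concerns only patients switched to adalimumab, and 6.5 gives no such figure for secukinumab.

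**Conclusion.** The point holds as an inconsistency in current protocol text on a named safety matter. The end points differ by 12 weeks (secukinumab, Week 44 against 56) or 10 weeks (adalimumab biosimilar, Week 46 against 56) for T2T patients dosed on schedule. The difference is longer for a patient who stops treatment early and stays in the study. No precedence is stated, and the 12-week end point is shorter than the elimination time given in 6.5.

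This rests on two assumptions: that participation ends at the Week 56 visit, as 9.2 implies, and that the 4 months are counted from the last adalimumab dose.

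Three larger conclusions are not supported.

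- The planned T2T arm of 150 is not a count of patients at risk. The documents do not say how many might be offered a live vaccine in these weeks.
- Efficacy conclusions are not touched on this account. For patients dosed on schedule the interval opens at Week 44 or later, after the Week 24 primary endpoint.
- Nothing here shows that either end point is clinically wrong, and this review does not choose between them.

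**What to change.** The sponsor should reconcile exclusion criterion 22 (section 5.2 and the summary copy), section 6.2.2.2 including Table 6-2, and section 6.5 so that all state one end point for the live-vaccine restriction. That end point should be consistent with the elimination statement in 6.5. The wording should also give a clear date for patients who stop treatment early, where the two rules lie furthest apart. The choice of end point belongs to the sponsor.

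The cost is protocol wording and a memo to sites. No visit, procedure or analysis changes. The downside is that some sites may have to change the vaccination advice they give during follow-up.
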